Specific Aims

To complete a 40 subject clinical study with the following aims:

1. To vaccinate healthy elderly with two distinct pneumococcal vaccines, collect longitudinal blood samples and assess pneumococcal-specific antibody responses.
2. To establish the transcriptional and epigenetic profiles of elderly blood immune cells linked with antibody responses to pneumococcal vaccination.
3. To examine the functional status of immune cells in the elderly stratified according to their pneumococcal vaccine responder status.

Design and Outcomes

This is a prospective, single-site, randomized, then open-label study designed to develop a detailed transcriptional and epigenetic profile of the immune response to pneumococcal vaccination with conjugated and non-conjugated polysaccharide vaccines in the senescent immune system of older adults.

Sample Size, Population, Interventions and Duration

In this study, 40 healthy adults ages 60 and older that have never received pneumococcal vaccination, will be randomized in a 1:1 ratio to receive Prevnar-13 (Pfizer), a conjugated 13-valent vaccine or Pneumovax 23 (Merck), a non-conjugated 23-valent vaccine. Following randomized assignment of vaccine, the study will be open-label.

Six (6) study visits will occur over about 70 days, with an optional 7th visit for participants to receive a second vaccination with the other pneumococcal vaccine one to two years after randomization. Participants will provide blood samples for transcriptional, epigenetic and biological analyses pre- and post-vaccination.

1 OBJECTIVES

The goal of our project is to assess the alterations to immune blood cells associated with the response of healthy elderly subjects to two pneumococcal vaccines, unconjugated (PPSV23) and conjugated (PCV13) polysaccharide vaccines. APCs, Tfh and B-cell subsets will be analyzed at different time points after vaccination. Phenotype, function, transcriptome and epigenetic analyses will be carried out on selected high responders and non-responders. These studies would provide us with the unique opportunity to investigate the human immune response of elderly individuals—a primary target for these vaccines—to a TI and TD antigen. Furthermore, a detailed

assessment of circulating immune cells from healthy elderly could enable us to identify the immune deficits that underpin non-responsiveness; such insights could help to improve vaccine efficacy.

Our detailed analyses will include: i) RNAseq of whole blood and cell subsets, to generate profiles of both coding RNAs and ncRNAs [1]; ii) ATACseq, to assess chromatin state and determine whether the genome is poised towards specific immune responses; and iii) *in vitro* cellular immunology studies to determine the function of APCs, T cells and B cells in vaccine-induced immune responses. We will keep all samples to further assess genotype using high-density SNP chips. Note that this study is not designed to establish baseline phenotypes predictive of vaccine responsiveness.

We expect to find that PPSV23 and PCV13 will activate different pathways leading to pneumococcal-specific antibody responses. Our hypothesis is that the PCV13 response pattern will resemble the response pattern we observed with Fluzone® inasmuch as both vaccines are considered to be TD. Significant differences in responsiveness can, however, be brought by molecular components specific to each vaccine, i.e., the polysaccharide component of PCV13 or the viral nucleic acids that might be included in Fluzone®. Our preliminary data *in vivo* in young adult volunteers and *in vitro* with APC subsets suggest that PPSV23 might trigger different immune pathways to elicit specific antibody responses. While the consensus is that its effects are TI, our observed induction of activated T cells *in vivo* and the presence of mutated IgG and IgA hints to more complex mechanisms, which might include both TD and TI mechanisms of B-cell activation [2].

[figure not shown]
1.1 Specific Aim 1

To vaccinate healthy elderly with two distinct pneumococcal vaccines, collect longitudinal blood samples and assess pneumococcal-specific antibody responses.

Hypothesis: We hypothesize that PPSV23 and PCV13 differentially activate the circulating immune cells and the blood transcriptome of healthy elderly individuals.

Rationale: Our studies in healthy young adults showed that Fluzone® and pneumococcal vaccines activate different immune cell subsets *in vivo* (data not shown). In addition, we showed that individuals vaccinated with PPSV23 and Fluzone® display a different blood transcriptome at

day 1 (Fig. 1). Thus, different vaccines might induce the generation of specific antibodies through different mechanisms. Here, our goal is to generate profiles of responses to conjugated and unconjugated polysaccharide-based pneumococcal vaccines and to correlate the elicited immune profiles with antibody responses.

Approach: The overall flow of the work is illustrated in Fig. 1. We will examine whether the induction of pneumococcus

Figure 1. Overview of work.

serotype-specific antibodies at day 28 correlates with the activation of T cells (as measured by flow cytometry) at day 10 and the activation of APCs at day 1 (measured by flow cytometry and transcriptomics). In a cohort of 40 healthy elderly naïve to pneumococcal vaccination we will: 1) vaccinate with either PPSV23 or PCV13; 2) longitudinally collect blood, serum and blood cell samples from each group; 3) perform the experiments that require immediate processing, such as flow cytometry analysis; and 4) cryopreserve all the other samples for downstream genomics and cellular immunology studies. Our earlier studies permitted us to draw robust conclusions on the transcriptome profiles in blood cells and on the role of Tfh activation in the generation of Fluzone®-specific antibody responses.

Elderly Populations: We will focus on the healthy adults >60 years of age that meet eligibility criteria (Section 4). 40 healthy community-dwelling elderly from areas surrounding the University of Connecticut Health Center will be accrued. Volunteers will be randomized to receive either the PCV13 or PPSV23 vaccine. CDC currently recommends that healthy older adults with no history of previous pneumococcal vaccination receive PCV13 followed by PPSV23 at least 12 months later. All participants will be offered a boost dose with the other vaccine at one to two years later, at no cost to them.

Rationale for selected time points: We will collect blood (50 ml) at days -7, 1, 10, 28 and 60

and (10 mL) on day 0 prior to vaccination with PPSV23 or PCV13 (**Table 1**).

Baseline (Day -7 and 0): Blood will be collected on these dates to assess baseline immune status. We will only collect 10ml of blood on day 0 so as to avoid collecting nearly 100ml on two consecutive days. **Day 1** coincides with the peak of the innate response to vaccines in blood. We found that PPSV23 induces a transcriptional signature reflecting the activation of

		Table 1. Sample processing details						
		Day	-7	0	1	10	28	60
Blood Volume			50 ml	10 ml	50 ml	50 ml	50 ml	50 ml
Ab titers				X			X	
Opsonophagocytic Assay				X			X	
Flow cytometry			X	X	X	X	X	X
CBC			X				X	
Cell sorting			X		X		X	X
	PBMC		X	X	X	X	X	X
	Monocytes		X		X			
ATAC-Seq	CD4 T cells		X			X	X	
	B cells		X			X	X	
	CD1c DCs		X		X			
	Whole blood		X	X	X	X	X	X
RNA-Seq	PBMC		X	X	X	X	X	X
	Monocytes		X		X			
	CD4 T cells		X			X	X	
	B cells		X			X	X	
	CD1c DCs		X		X			
In vitro studies	Tfh						X	
	B cells						X	

myeloid compartment. We will establish whether this transcriptomic signature is observed in elderly cohorts. **Day 10** is when T-cell responses (including Tfh cells) peak. This time point allows us to determine whether PPSV23/PCV13 also activates a Tfh subset in elderly and whether a lack of Tfh activation correlates with a lack of anti-pneumococcal antibody responsiveness as we showed with Fluzone®. The activation of CD4+ Tfh subsets will be measured as a function of ICOS expression levels in conjunction with CXCR5, CCR6 and CXCR3. In addition, a portion of the blood samples collected at day 10 will be used for transcriptome analysis. **Day 28 (± 3 days)** reflects the peak of the circulating antibody response. We will assess the induction of serotype-specific anti-pneumococcal antibody titers at days 28. **Day 60 (± 5 days)** will provide us with additional blood samples containing memory cells that can be used to eventually confirm the day 28 *in vitro* data. Details of sample processing are given in **Table 1**. We will cryopreserve PBMCs

and sorted cell populations for genetic and cellular immunology experiments at all time points. If cell yield prevents cryopreservation of PBMCs, we will recruit additional subjects to reach our proposed number of 40.

Antibody responses: We will analyze the breadth and magnitude of antibody responses by assessing PPSV23/PCV13 serotype-specific IgG titers at day 0 and 28, as recommended by the World Health Organization, and using the Opsonophagocytic assay. This assay (serotypes 4, 6B, 14 and 23F) will be performed using serotype-specific *S.pneumoniae* incubated with serial-diluted heat-inactivated sera [3]. Newborn rabbit serum is added as a source of complement and differentiated HL-60 cells are added. Sera are tested in duplicate and results obtained using the Opsotiter 1 software. We will use U-scores to rank antibody response by titer, affinity and number of serotypes (as done for antigen-specific T cells in response to DC vaccines [4-6]. Our collaborator, [name], will assess serotype-specific anti-polysaccharide responses. His lab will also measure antibody avidity and opsonizing capacity as described [7].

CMV status. Influenza vaccine studies in the elderly have revealed a critical role for CMV status [8]. In a single study, CMV status did not appear to influence antibody responses to PPSV23 vaccine in older adults, yet its role in other aspects of immune responses or in baseline pre-vaccination status cannot be ruled out[9]. As a result, we will obtain CMV status using antibody titers and PCR-based technologies [10], and will include this variable in our analytic plan.

Analytical Approaches:

1. *Multicolor flow cytometry*: 0.5 ml of blood will be used to determine the profile of circulating immune cells. We designed five multi-color monoclonal antibody cocktails that will permit us to establish the detailed phenotype of T-cell subsets, monocytes, DCs and B-cell subsets. We included a set of antibodies to identify NKT cells, as these cells have been reported to contribute to responses to PPSV23 vaccination [11].

2. *Cryopreservation of isolated PBMCs and sorting of purified populations*: We have validated monoclonal antibody cocktails that permit us to sort T-cell subsets, monocytes, DCs and B cells for cryopreservation (**Table 1**). PBMCs will be frozen in 4–5 aliquots (recovering on average 20×10^6 cells); 1–2 will be used for ATAC-seq and 2–3 for functional studies. After thawing we will sort monocytes, CD1cDCs, CD45RO+CD4+ T cells, and B cells for ATAC-seq and RNA-seq. We aim to collect 15,000–25,000 of each type of cells.

3. *Cryopreservation of whole blood RNA*: Two Tempus tubes (1 ml each) will be stored for further analysis of coding RNA and ncRNAs.

4. *Sample prioritization*: Our preliminary data show that we can perform ATAC-seq on cryopreserved cells. Previous studies [12] show that T/B-cell cultures can be done with cryopreserved and thawed cell samples. If we encounter low cell yields, which might limit the cell culture experiments, we can draw from the blood samples acquired at day 60.

1.2 Specific Aim 2

To establish the transcriptional and epigenetic profiles of elderly blood immune cells linked with antibody responses to pneumococcal vaccination.

Hypothesis: We hypothesize that transcriptome and epigenome profiling of blood and sorted Protocol Version 5.1, 9 July 2019 Page 7 of 45

immune cells will reveal the coding and non-coding regulatory sites associated with different immune responses following vaccination with PPSV23 and PCV13 in healthy elderly.

Rationale: The non-coding regions of the genome contain a variety of RNA species, such as microRNAs (miRNAs) and long non-coding RNAs (lncRNAs), which play fundamental roles in regulating gene expression [1, 13, 14]. The study of these regulatory RNAs is becoming increasingly relevant to the fields of immunology and aging. Recent studies in aging mice and humans reported the up- and downregulation of miRNA expression in PBMCs among other tissues [15, 16], yet little is known about the status of ncRNAs within elderly immune cells, particularly in response to vaccination. In addition to transcriptome differences, it is conceivable that epigenetic remodeling also contribute to decline in the immunity of elderly. Current epigenetic approaches require large numbers of cells, making them impractical for detailed analysis of primary blood-derived human immune cells. In a recent major advance, a transposase-based method to sequence genomes, ATAC-seq, was adapted to interrogate chromatin accessibility. ATAC-seq generates representative chromatin accessibility maps from as few as 500–5,000 cells, making it an ideal approach to investigate genome-wide epigenetic patterns at coding and noncoding regulatory sites in primary human immune cell samples.

To investigate our hypothesis we will apply RNA-seq, rather than DNA microarrays, to generate transcriptional profiles, as this will enable quantitative assessment of both coding RNAs and ncRNAs. We will also use ATAC-seq to resolve the epigenetic landscape of immune cells in healthy elderly in the context of vaccine responses.

Approach:

1. *Blood transcriptomics by RNA-seq:* We will carry out RNA-seq of whole blood samples at baseline, day 1 and day 10. Samples collected from days 28 and 60 will be kept frozen for future studies. RNA-seq on purified cell subsets will be performed using purified cells from the five lowest and five highest responders for each vaccine. Sequencing will be performed at JAX-GM with an Illumina HiSeq2500.
2. *Blood epigenomics analysis by ATAC-seq:* We will analyze PBMCs, CD4+ T cells, monocytes, CD1cDCs and B cells (25×10^3 cells per assay). We are also developing assays with lower cell numbers to address the scarcity of some populations, and are encouraged by reports of single cell ATAC-seq [17]. We will generate a database describing the DNA accessibility landscape of major immune-cell subsets from elderly individuals at steady state. The data will also include the DNA accessibility landscape of monocytes, T and B cells analyzed at different time points following vaccination with the two pneumococcal vaccines. For these in-depth studies, we will select the five highest and five lowest responders for each vaccine.

Correlative analysis: We will correlate the increased levels of day 28 anti-pneumococcal antibodies as defined in Aim 1 with all the parameters collected in this aim. Parameters include: 1) cellular composition at baseline, day 1 and day 10 post-vaccination; 2) transcriptome analysis on blood and purified immune cell subsets at baseline, day 1 and day 10; 3) ATAC-seq data on PBMCs and purified cell subsets at the different time points and 4) pneumococcal colonization at baseline and at day 28. A detailed description of the statistical approaches is given below (see Integrative Data Analysis section).

1.3 Specific Aim 3

To examine the functional status of immune cells in the elderly stratified according to their pneumococcal vaccine responder status.

Hypothesis: We hypothesize that lack of *in vivo* response to PPSV23 and PCV13 depends on alterations to APCs, Tfh cells or B cells.

Rationale: Aging impacts the immune system at steady state as well as its capacity to respond to challenges such as infection or vaccination. In advanced age, there are i) reduced numbers of B cells responding to influenza as well as lower antibody avidity to carbohydrate antigens [18-22] and ii) increased numbers of memory cells occupying tissue niches that is linked with lower migration and maintenance of naïve B and T cells into tissues. These changes, associated with the biased differentiation of CD4+ T-cells into Th17 cells, diminish the overall capacity of CD8+ and CD4+ cells to mount diverse and robust responses to antigens [23, 24]. Nonetheless, major gaps remain in our knowledge of elderly T/B-cell responses. There is also a need to better understand the alterations in function of innate immune cells including DCs and macrophages in advanced age. We propose two sub-aims to further characterize the functions of key immune cell types in the healthy elderly, thereby complementing the genomics and epigenomics data gathered in Aim 2.

Aim 3a: Determine whether a specific immune-cell subset can be linked with the lack of response to pneumococcal vaccines. Here, we will seek to determine whether *ex vivo* responses to vaccines can be related to *in vivo*-derived transcriptional profiles of the blood at steady state and after vaccination as well as to antibody responses. We will analyze PBMCs and sorted monocytes, CD1c+DCs, CD4+ T cells and B cells.

PBMC function: We will activate PBMCs from five of each of PPSV23 and PCV13 responders and non-responders with medium alone, PPSV23 or PCV13. PMA plus ionomycin and lipopolysaccharide (LPS) will be used as positive controls. We will measure cell activation by flow cytometry at day 1 and 2. We will measure cytokine production at day 2 (IL-1, IL-6, IL-10, IL-21, TNF and IFNg) post-stimulation. Specific antibody levels will be measured at day 12 as described [3, 20, 25]. Some experiments will be carried out by culturing PBMCs with a few selected polysaccharides from *S. pneumoniae*, such as PP13 and PP23F [18, 20, 21].

Monocyte and CD1c+DC function: we will select baseline monocytes/CD1c+DCs from five elderly subjects not responsive to PPSV23 and five not responsive to PCV13 and compare them to monocytes/CD1c+DCs from responders. Monocytes/CD1c+DCs will be isolated using CD14-beads and cultured in medium, with either of the two pneumococcal vaccines or LPS as an activation control. Before and after stimulation we will:

- 1) Determine the phenotype of cultured cells by flow cytometry at day 1 post-activation using various markers, including MHC class-II, CD40, 80, 83 and 86.
- 2) Measure the secretion of cytokines (IL-1, IL-6, TNF and IL-10) by ELISA.
- 3) Assess the transcriptome of monocytes after six hours of activation using RNA-seq.
- 4) Analyze monocyte differentiation into either DCs or macrophages following culture with GM-CSF with or without IL-4 [26]. We will measure the differentiation potential of the elderly

monocytes by assessing the phenotype of cultured cells and analyzing their ability to induce a mixed lymphocyte reaction with allogeneic CD4+T cells. We will also measure, after six days of co-culture, the production of cytokines by flow cytometry after activation with PMA and ionomycin [27-29]. Cytokines to be measured include IL-21 and CXCL-13, which are specifically secreted by Tfh cells; IFN-g (Th1); IL-4 (Th2) and IL-17 (Th17). CD1c+DC function will be measured as described for monocytes [30, 31].

B-cell function: B cells will be isolated from PBMCs by magnetic sorting and will then be cultured with the vaccines alone or together with SAC (i.e., fixed *Staphylococcus aureus* strain Cowan) and IL-2 [32, 33]. Alternatively we will use a combination of CD40-L and either IL-10 or IL-21, which results in potent cell proliferation and differentiation into plasma cells [34]. Ig secretion will be measured at day 12 by ELISA. Differentiation into plasma cells will be assessed by loss of CD20 and acquisition of CD138 [35].

Aim 3B: Determine whether the CD4+T cells can induce B cells to differentiate into plasma cells secreting anti-pneumococcal antibodies *in vitro*.

For these studies, we will use day 28 and day 60 cells from vaccine responders versus non-responders.

Assess antigen specificity of T-cell subsets: We will use cultures of purified CD4+ T-cells and B cells as we described. Briefly, purified CD4+T cells will be cultured with either of the two vaccines or a mixture of the polysaccharides (ATCC) for which the elderly showed an antibody response. For the PCV13 cohort we will also test the reactivity to protein carrier alone (CRM 197 from LBL). T-cell activation with selected antigens can be measured by induction of CD154 after six hours of culture in the presence of monensin and brefeldin[12]. Cytokine expression will be assessed by flow cytometry after intracytoplasmic staining with anti-IFNg, IL-2, IL-10, IL-17 and IL-21 as described. A second set of experiments will be carried out with separated CXCR5+CD4+CD45RO+ T cells (Tfh cell) or CXCR5-CD4+CD45RO+ T cells (non-Tfh cells).

Assess T-cell subset helper activity in B cells: To analyze the ability of T cells to activate B cells, we will use a dual approach as designed for Fluzone®-vaccinated individuals. Purified T-cell subsets (5×10^3 per well) will be cultured with sorted naïve (IgD+CD27-CD3-) or memory (CD27+CD3-CD19+) B cells (5×10^3 per well) in the presence of 1ug/ml staphylococcal enterotoxin B to test polyclonal B-cell activation and differentiation. Experiments will also be carried out with purified IgM+ memory B cells. B-cell activation will be monitored by induced expression of CD138 and CD38 after 14 days of culture. Culture supernatants will be harvested at day 14 for measurement of IgM, IgG and IgA by ELISA. For antigen-specific responses, memory B cells will be loaded with the relevant antigen and cultured for six days with the Tfh and non-Tfh CD4+ T-cell subsets as shown earlier. Supernatants will be harvested at day 14 and assessed for anti-pneumococcal polysaccharide antibodies by ELISA.

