II) ADAPTIVE IMMUNE RESPONSES TO VACCINATION. To begin to define the cell types that comprise adaptive immune responses to vaccination, we performed detailed phenotypic analyses of T-cell subsets taken from healthy young adults vaccinated or not with Flu or PPSV23 vaccine. We found that vaccination induced ICOS expression almost exclusively on blood CXCR3⁺ Tfh cells and that the induced ICOS⁺CXCR3⁺ Tfh cell population was enriched with cells specific for Flu antigens. The increase in ICOS⁺CXCR3⁺ Tfh cells in blood at day seven post-vaccination correlated with an increase in antibody titers at Day 28. Isolated ICOS⁺CXCR3⁺ Tfh cells induced antigen-loaded memory B cells to produce Flu-specific Abs *in vitro* through secretion of IL-10 and IL-21. Thus, the analysis of blood Tfh subsets led us to discover biomarkers reflecting vaccine efficacy and provided insights into vaccine mode of action. Further studies in healthy young adults vaccinated with PPSV23 indicated 1) a plasmablast response on days 7 and 10 and 2) the emergence of ICOS⁺ Tfh cells in blood peaking at day 10. However, the status of Tfh cells in elderly has not been well characterized. We will address this gap by profiling the Tfh cells of healthy elderly vaccinated with either PPSV23 or PCV13.

III) IMMUNOGENOMICS OF BLOOD CELLS FROM OLDER ADULTS. We recently launched a systematic analysis of the status of immune cells in the blood of elderly subjects (age 65 and older; mean=75.3 yrs). Our approach included 1) assessment of cell composition by polychromatic flow cytometry; 2) transcriptional profiling by RNA-seq and 3) assessment of epigenetic landscape of PBMCs as well as sorted subsets by ATAC-seq (Assay for Transposase Accessible Chromatin or ATAC-Seq)[82]. ATAC-seq captures open (i.e., transcriptionally active) chromatin sites and can be used to reveal various categories of epigenetic information, including the genomic locations of open and closed chromatin regions and their interplay with DNA-binding proteins, as well as of individual nucleosomes. Importantly, ATAC-seq generates information *via* a simple two-step protocol that requires only a few thousand cells, making it uniquely suited to study epigenomic profiles of human clinical samples with a systems biology approach, where small cell numbers are a limiting factor.

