8 INTEGRATIVE DATA ANALYSIS

8.1 Statistical Methods

The breadth and magnitude of IgG titers will be analyzed individually and together using best-response and multivariate U-statistic approaches [4, 97]. Differences among groups (e.g., responder status) and/or time of immunological variables (e.g., flow, RNAseq) will be assessed using generalized linear mixed-model analyses with appropriate distributional assumptions (e.g., normal, negative binomial) and link functions (e.g., identity, log). Propensity scores [98] will be adjusted for possible confounds such as gender, age, race and ethnicity, while the Bonferroni correction or Benjamini and Hochberg false discovery rate (FDR) will account for multiple testing [99]. Correlation of clinical and immunological variables will be conducted using the Pearson or Spearman Correlation Coefficient depending on whether or not the assumptions of linearity and homoscedasticity are met. For class prediction, a variety of methods including k-nearest neighbors, radial basis machine, random forests, boosted trees and support vector machines will be employed and validated using leave-one-out cross-validation. Unsupervised analysis of high dimensional data will be conducted using heatmaps, hierarchical cluster analysis and principal component analysis. Lastly, attrition and missing data are issues in longitudinal [100] and elderly studies [101]. "Missingness" will be characterized and multiple imputation applied when appropriate [102-104]. Drs. [name] (JAX) and [name] (SIDRA) will assist with statistics and bioinformatics as needed.

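### The planned correlation of antibody induction with Day 1 and Day 10 activation does not say whether activation is a level or a change, and has no baseline term although pre-vaccination values are collected

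*Combined protocol and SAP*

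**What the plan says.** The goal stated in section 1.1 is "to correlate the elicited immune profiles with antibody responses". The Approach paragraph makes this specific: does induction of serotype-specific antibody at Day 28 show a relation that "correlates with the activation of T cells (as measured by flow cytometry) at day 10 and the activation of APCs at day 1"? Under the rationale for time points, "The activation of CD4+ Tfh subsets will be measured as a function of ICOS expression levels in conjunction with CXCR5, CCR6 and CXCR3". The same paragraph says of Day -7 and Day 0 that "Blood will be collected on these dates to assess baseline immune status", and Table 1 marks flow cytometry and whole-blood RNA-seq on both days. Sorted subsets have Day -7 only.

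The correlative analysis in section 1.2 lists the parameters to be set against the rise in antibody, among them "cellular composition at baseline, day 1 and day 10 post-vaccination", and likewise the transcriptome at those times. They appear as separate items.

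On method, section 8.1 says "Correlation of clinical and immunological variables will be conducted using the Pearson or Spearman Correlation Coefficient", the choice resting on linearity and homoscedasticity. Its generalized linear mixed model is assigned to differences between groups and over time.

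The sponsor's influenza work, in the second part of the preliminary studies in section 2.1, found that the increase in ICOS+CXCR3+ "Tfh cells in blood at day seven post-vaccination correlated with an increase in antibody titers at Day 28".

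**The concern.** A Day 10 measurement is the person's usual level plus whatever vaccination added. The stated interest is in the second part only. A two-variable coefficient on the day value cannot separate the two.

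Two errors can follow. Spread between people that existed before vaccination weakens a real link between induced activation and antibody. Conversely, a standing trait related to antibody response can be reported as activation, although section 1 says the study is not designed to find baseline phenotypes that predict response.

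The antibody side has a Day 0 reference, since titers are taken on Days 0 and 28. The cell side has none inside the stated correlation. Leaving level or change open also allows the choice to be made after the data are seen, across many cell subsets and transcripts with 20 people per vaccine.

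**Working it through.** **The plan's own figure.** Section 8.2 gives no power for this correlation. Its only figure is more than 90% power, with 20 per cohort, to detect at least 6,000 differentially expressed genes. Taking a two-fold difference as 1 on the log2 scale, SD 0.7 and FDR 1%, the per-gene level is 6,000 × 0.9 × 0.01 / ((37,649 − 6,000) × 0.99) = 0.00172. The normal approximation then gives 91.7%, which agrees with the plan (the exact t-test gives 86.2%). That figure concerns gene-wise differences and does not bear on this point. For a correlation, the smallest r detectable with 80% power is tanh((1.96 + 0.84)/√(n − 3)): 0.59 at n = 20 and 0.43 at n = 40.

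**Inputs.** From the documents: 20 per vaccine, pre-vaccination values on Days -7 and 0, and a plain correlation coefficient. Assumed, because the documents give nothing: a true correlation of 0.6 between induced change and antibody, measurement error SD 0.3, a two-sided 5% test, and the ratio R of the baseline SD to the SD of the change. The SD of the change is set to 1.

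**Model.** Stable level B (SD R), induced change C (SD 1), independent of each other.
- Day value = B + C + error.
- Baseline = mean of two readings of B + error.
- True link: antibody = 0.6·C + 0.8·noise.
- No induced link: antibody correlates 0.5 with B and 0 with C.

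**Correlations implied by the model.** With a true link, the day value has r = 0.6/√(R² + 1 + 0.09), which is 0.56, 0.52, 0.42 and 0.27 for R = 0.25, 0.5, 1 and 2. The change from the mean of two baselines has r = 0.6/√(1 + 0.09 + 0.045) = 0.56 at every R. With no induced link, the day value still has r = 0.5·R/√(R² + 1.09), which is 0.22, 0.35 and 0.44 for R = 0.5, 1 and 2.

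**Simulation, 20,000 trials of n = 20.** Adjusted means the partial correlation given baseline.

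| R | True link: power, day value | True link: power, adjusted | Baseline link only: significant, day value | Baseline link only: significant, adjusted |
|---|---|---|---|---|
| 0.25 | 76% | 75% | – | – |
| 0.5 | 68% | 75% | 15% | 5-6% |
| 1 | 46% | 75% | 33% | 5-6% |
| 2 | 21% | 75% | 52% | 5-6% |

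Hand check at R = 1: atanh(0.415) × √17 − 1.96 = −0.14, which is a power of about 44% and close to the simulated 46%.

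**If baseline and change are correlated** (true link):
- R = 0.5, correlation +0.4: day value 74%, adjusted about 69%.
- R = 1, +0.4: 63% v 68%.
- R = 1, −0.4: 28% v about 67%.

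**A second set of assumptions.** Fix the true variance of the day value at 1, with a stable share of 0.2, 0.5 or 0.8, error variance 0.1 and a single baseline reading. With a true link of 0.6, power at n = 20 is 64%, 42% and 19% for the day value, and 71%, 65% and 48% adjusted. The adjusted figure also falls here because the induced part shrinks relative to the error. With a link of 0.6 to the stable part only, the day value is significant in 19%, 42% and 64% of trials, against 7-8% adjusted and 5% for the change score. With error variance 0.3, adjustment on one noisy baseline leaves 10-13%. With a stable share of 0.2 and error variance 0.3, the change score does slightly worse than the day value under a true link (r = 0.45 v 0.47), while the adjusted r is 0.49.

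**The case against.** A reader might infer that the sponsor chose the level over the change. The documents do not support that. They speak of activation, induction and elicited profiles. Section 1.1 also presents the Day 10 Tfh analysis as a repeat of the Fluzone finding, which used the increase in Tfh cells. A mention of ICOS expression levels can name the marker without fixing the quantity analysed. The plan is silent on the choice.

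A reader might also infer that baseline plays no part at all. Section 1.2 contradicts this: baseline composition and transcriptome are themselves correlated with antibody. A baseline trait that drives response could therefore show up beside the Day 10 result, which softens the risk of mimicry. It does not remove it, since two separate coefficients do not show whether the Day 10 link survives once baseline is accounted for.

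The mixed model in 8.1 could include a responder-status-by-time contrast, which compares within-person change. The wording permits this but does not specify it, and the model is not the antibody correlation.

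The size depends on unknown ratios. Section 2.1 describes ICOS+ Tfh cells emerging after vaccination, which suggests, without proving, a low starting level for that marker. If so, little is lost by using the level. The 5% tests are also not the plan's rule, since 8.1 applies Bonferroni or FDR. Finally, this is exploratory profiling with no power claim for the correlation. These points limit the size and weight of the concern. They do not supply the missing definition or the baseline term.

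**Conclusion.** The concern holds as one of specification. The plan relates antibody induction to Day 1 and Day 10 activation by a two-variable coefficient, does not define activation as level or change, and has no baseline term in that correlation even though the baseline is collected.

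If the day value is used, which is the plainest reading of the text, the loss ranges from nothing to severe. Under the first model, power is 76% v 75% at an SD ratio of 0.25 and 21% v 75% at a ratio of 2. False attribution of a baseline link runs from about 15% to 52% over ratios 0.5 to 2, against 5-6% adjusted. A positive correlation between baseline and change can give the level a small advantage (74% v about 69% at ratio 0.5).

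All of this rests on assumed ratios, error and true correlations, and on n = 20 with unadjusted 5% tests. None of it applies to the sorted-cell data, which come from the five highest and five lowest responders per vaccine. The change is worth making before analysis because it is nearly free and matches the stated goal. It does not call the trial's conduct or data into question.

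**What to change.** In 1.1, 1.2 and 8.1, state that the main correlation with antibody induction uses the Day 1 or Day 10 value adjusted for the same person's pre-vaccination value. This can be a partial correlation, or a regression with baseline as covariate, on the log scale. Use the mean of Day -7 and Day 0 where both exist, which reduces the bias left by a noisy baseline. Analyse within vaccine arm, under the multiplicity correction already planned.

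Report the log change from baseline as a sensitivity analysis. Keep the unadjusted level correlations, including the baseline one, as descriptive. For sorted-cell data use Day -7 as the baseline, and say that these results come from selected extremes.

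The cost is wording, one degree of freedom per correlation, and a small loss of power if baseline spread proves low. No extra blood, visit or assay is needed.
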